5.2 Use of co-intervention

Not applicable.

5.3 Escape medication

Not applicable.

Table 1 Example menu month 1-3

Koolhydraatbeperkt (35 g/dag) & energiebeperkt (1500 kcal, adequaat eiwit (0.8 g E/kg))

Gemiddeld gewicht (80 kg)		Energie (kcal)	Eiwit totaal (g)	Vet totaal (g)	Koolhydraten totaal (g)
Ontbijt					
Brood, koolhydraatarm Of vervanging zie variatielijst	1 snee (= 35g)	84	6,0	3,1	5,0
Margarineproduct 60% vet <17 g verz vetz ongeze	5g	27	0,0	3,0	0,0
48+ kaas of vleeswaar, stukje vis of 0,5 gekookt ei	1 voor 1 snee (= 20g)	74	4,6	6,1	0,0
Thee zonder suiker	2 bekers (=500g)	0	0,0	0,0	0,0
Subtotaal		185	10,6	12,2	5,0
In de loop van de ochtend					
Aardbeien of ander fruit	50g	14	0,3	0,0	2,5
Thee/koffie zonder suiker	2 bekers (= 500ml)	0	0,0	0,0	0,0
Subtotaal		14	0,3	0,0	2,5
Middagmaaltijd					
Brood, koolhydraatarm of vervanging zie variatielijst	1 snee (= 35g)	84	6,0	3,1	5,0
Margarineproduct 60% vet <17 g verz vetz ongeze	5g	27	0,0	3,0	0,0
Maaltijdsalade van IJsbergsla	1,5 schaaltje (= 70g)	10	0,6	0,2	1,1
Zalm, gerookt of ander vis	25g	46	5,5	2,7	0,0
Cherrytomatje, rauw	4 stuks (= 40g)	12	0,4	0,3	1,6
Komkommer zonder schil	25g	3	0,1	0,1	0,5
Avocado	50g	100	0,9	9,8	0,9
Dressing van: Olie, alle soorten	1,5 eetlepel (= 15g)	134	0,0	14,9	0,0
Mayonaise	0,5 eetlepel (= 10g)	66	0,1	7,2	0,4
Subtotaal		482	13,6	41,3	9,5
In de loop van de middag:					
Noten, gemengd, ongezouten	1 handje (= 25g)	162	5,3	13,8	3,4
Thee/koffie zonder suiker of suikervrije frisdrank	2 bekers(=500ml)	0	0	0	0
Avondmaaltijd					
Aardappelen, gekookt	28g	24	0,5	0,1	5,0
Groente, gekookt	140g	43	2,7	0,7	5,0
Kipfilet, vlees of vis, onbereid	1 stuks (= 125g)	136	29,1	2,3	0,0
Bereiden in Olie, alle soorten	1,5 eetlepel (= 15g)	134	0,0	14,9	0,0
Margarine, vloeibaar, ongezouten	0,5 eetlepel (= 5g)	37	0,0	4,1	0,0
Subtotaal		374	32,3	22,1	10,0
In de loop van de avond					
Griekse yoghurt, vol	125g	156	5,9	12,5	4,5
Olie, alle soorten Bijvoorbeeld kokosolie	1,5 eetlepel (= 15g)	134	0,0	14,9	0,0
Thee/koffie zonder suiker /water of sv frisdrank	2 bekers (500ml)	0	0	0	0
Subtotaal		290	5,9	27,4	4,5
Totaal	2000ml	1507	68	116,8	34,9

Table 2 Example menu month 4-6.

Koolhydraatbeperkt (60 g/dag) & energiebeperkt (1500 kcal, adequaat eiwit (0.8 g E/kg))

Gemiddeld gewicht (80 kg)		Energie (kcal)	Eiwit totaal (g)	Vet totaal (g)	Koolhydraten totaal (g)
Ontbijt					
Brood, koolhydraatarm Of vervanging zie variatielijst	2 sneden (=70g)	169	12,0	6,2	10,0
Margarineproduct 60% vet <17 g verz vetz ongez	2 x 5 gram	11	0,0	1,2	0,0
48+ kaas	1 voor 1 snee (=20g)	74	4,6	6,1	0,0
Vleeswaren, gemiddeld Vis of ei	1 voor 1 snee (=20g)	35	2,4	2,7	0,4
Thee zonder suiker	2 bekers (=500g)	0	0,0	0,0	0,0
Subtotaal		289	19,0	16,2	10,4
Ochtend					
1 stuks Fruit (geen banaan of druiven)	150 g	74	1,2	0,0	16,5
Thee zonder suiker	2 bekers (=500g)	0	0,0	0,0	0,0
Subtotaal		74	1,2	0,0	16,5
Middagmaaltijd					
Brood, koolhydraatarm Of vervanging zie variatielijst	2 sneden (=70g)	169	12,0	6,2	10,0
Margarineproduct 60% vet <17 g verz vetz ongez	2 x 5 gram	11	0,0	1,2	0,0
48+ kaas	1 voor 1 snee (=20g)	74	4,6	6,1	0,0
Vleeswaren, gemiddeld Vis of ei	1 voor 1 snee (=20g)	35	2,4	2,7	0,4
Thee zonder suiker	2 bekers (=500g)	0	0,0	0,0	0,0
Subtotaal		289	19,0	16,2	10,4
Middag					
Noten, gemengd, ongezouten	1 handje (=25g)	162	5,3	13,8	3,4
Thee zonder suiker	2 bekers (=500g)	0	0,0	0,0	0,0
Subtotaal		162	5,3	13,8	3,4
Avondmaaltijd					
Aardappelen, gekookt	1 klein (=50g)	43	0,9	0,2	8,9
Groente, gekookt	3 opscheplepels (= 150 g)	46	2,9	0,8	5,4
Kipfilet, vis of vlees onbereid	1 stuks (=125g)	136	29,1	2,3	0,0
Olie, alle soorten	1,5 eetlepel (=15g)	134	0,0	14,9	0,0
Margarine vloeibaar 80% vet	0,5 eetlepel (=5g)	37	0,0	4,1	0,0
Subtotaal		396	32,9	22,3	14,3
In de loop van de avond					
Griekse yoghurt, vol Hieraan toevoegen:	125 g	156	5,9	12,5	4,5
Olie, alle soorten Bij voorkeur kokosolie	1,5 eetlepel (=15g)	134	0,0	14,9	0,0
Thee zonder suiker	2 bekers (=500g)	0	0,0	0,0	0,0
Subtotaal		290	5,9	27,4	4,5
Totaal	2000 ml	1500	83,3	95,9	60,0

6. INVESTIGATIONAL PRODUCT

Not applicable, this study does not involve an investigational product.

6.1 Name and description of investigational product(s)

Not applicable, this study does not involve an investigational product.

6.2 Summary of findings from non-clinical studies

Not applicable, this study does not involve an investigational product.

6.3 Summary of findings from clinical studies

Not applicable, this study does not involve an investigational product.

6.4 Summary of known and potential risks and benefits

Not applicable, this study does not involve an investigational product.

6.5 Description and justification of route of administration and dosage

Not applicable, this study does not involve an investigational product.

6.6 Dosages, dosage modifications and method of administration

Not applicable, this study does not involve an investigational product.

6.7 Preparation and labelling of Investigational Medicinal Product

Not applicable, this study does not involve an investigational product.

6.8 Drug accountability

Not applicable, this study does not involve an investigational product.

7. NON-INVESTIGATIONAL PRODUCT

Not applicable, this study does not involve a non-investigational product.

7.1 Name and description of non-investigational product(s)

Not applicable, this study does not involve a non-investigational product.

7.2 Summary of findings from non-clinical studies

Not applicable, this study does not involve a non-investigational product.

7.3 Summary of findings from clinical studies

Not applicable, this study does not involve a non-investigational product.

7.4 Summary of known and potential risks and benefits

Not applicable, this study does not involve a non-investigational product.

7.5 Description and justification of route of administration and dosage

Not applicable, this study does not involve a non-investigational product.

7.6 Dosages, dosage modifications and method of administration

Not applicable, this study does not involve a non-investigational product.

7.7 Preparation and labelling of Non-Investigational Medicinal Product

Not applicable, this study does not involve a non-investigational product.

7.8 Drug accountability

Not applicable, this study does not involve a non-investigational product.

8. METHODS

8.1 Study parameters/endpoints

8.1.1 Main study parameter/endpoint

Our main study endpoint is the difference in tumour regression. The size (largest diameter in cm) of the largest hepatocellular adenoma found on MRI will be measured at T_0 = time of inclusion and at T_5 = 6 months after start of the intervention. Mean regression will be calculated after which it will be compared to the regression in tumour size of our (earlier acquired) cohort and the subsequent internally validated model published earlier (30).

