3. STUDY DESIGN

We aim to answer our research questions by conducting a single-centre, proof of concept interventional matched cohort study.

Main study population

Our newly acquired cohort will be compared with a matched historical control group acquired during an earlier study (30). This large multicentre retrospective cohort developed a prediction model for patients with HCA (N=180, HCA diameter at baseline: 82.0mm (65-100) and follow-up: 65.0mm (56-80) (Median (IQR)). This prediction model estimates the probability of HCA regression to <5cm at 1 and 2 years follow-up (30) with an internally validated c-index of 0.79.

The prediction model the authors developed was translated into a chance assessment tool. Included predictors in this model are: diameter at diagnosis, diameter at first follow-up, dates of diagnosis and first follow-up and HCA-subtype. This chance assessment tool will provide the estimated chance of regression to 0,5 cm at 1-2 years after diagnosis and is currently used in clinical practice at Erasmus University Medical Center. The chance tool is available via <https://hcaprediction.shinyapps.io/calculator/>. This prediction model will also be used for our included patients, as part of standard of care.

Matching to the earlier acquired patient cohort will be based on subject age, use of oral contraceptives, ethnicity, weight, type of HCA, size of HCA and number of lesions at baseline. Matching will be conducted via optimal nearest-neighbor matching on propensity score, in a 1:1 ratio without replacement (63). Examination of the balance on covariates resulting from the matching method will be conducted to determine if matching has been successful.

Study subpopulation

As a nested pilot-study we aim to acquire a small sub-cohort of subjects with a slightly different population base criterium, see chapter 4.1. The inclusion and exclusion criteria will be applied in the same way as in the main study population.

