8.1.3 Other study parameters

- Baseline subject characteristics such as age, sex, weight, length, BMI, oral contraceptive use, other medication use, comorbidities, size of hepatocellular adenoma at baseline, multiple or single lesion, amount of hepatocellular adenoma's at baseline, subtype of hepatocellular adenoma, time since initial diagnosis, time since last imaging study, imaging study provided (MRI/CT/Ultrasound), referring hospital and active pregnancy wish.
- Macronutrient intake (3-day food diary)
- Physical activity by IPAQ questionnaire (70, 71), Dutch version 1, 23-01-2011. Higher score means a higher level of physical activity
- Incidence of symptomatic HCA, defined as:
 - o HCA rupture/bleeding confirmed on CT / MRI
 - o for which admittance into the hospital or (endovascular) treatment is indicated.

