8.3 Study procedures

Standard procedure / current best clinical practice

Main study population

Subjects present themselves at our outpatient clinic after referral from a peripheral or other tertiary/university hospital. Subjects will be receiving additional imaging studies (f.i. an MRI) if the necessary imaging study has not been conducted at the peripheral/referring hospital, according to current standard protocol/clinical practice. Afterwards their case will be discussed in our multidisciplinary meeting, including a (liver) radiologist, hepatobiliary surgeon, gastroenterologist / hepatologist and dietician.

During current clinical practice, subjects will enter the "Wait and See" / "Active Surveillance" period for 6 months (30) based on several criteria. See figure 1 for the management flowchart.

Subpopulation

Subjects eligible for inclusion into the study subpopulation are already being treated via the outpatient clinic via active surveillance. After the initial 6 months of active surveillance (with advice consisting of cessation of use of oral contraceptives and aiming for weight loss), subjects have been subjected to an MRI. If this MRI shows no or only a minimal (5mm) reduction of the size of the HCA, patients are subjected to another active surveillance period of 6 months after which another MRI is performed. We want to provide the patients with the option to adhere to the ketogenic diet as a potential therapeutic option.

Intervention / Study procedure

Time of inclusion:

Eligible subjects visiting the outpatient clinic after discussion of their case in the multidisciplinary meeting are invited to participate in the study. The possible participant is asked whether she wants to be approached for further information on this study. The gastro-enterologist / hepato-biliary surgeon shortly explains the purpose of the study after which, if the subject agrees to it, the study investigator explains the study design and purpose in more detail. Subjects receive written information and are offered a reflection period of one week before they are contacted again about participation in the study. In case informed consent is given, subjects will receive an appointment with a dietician.

Follow-up and outpatient visits will be identical to normal procedure, except the extra appointments with the dietician and the additional blood samples drawn by venous puncture on T₀, T₃ and T₅.

Consultation by Dietician

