This consult will focus on explaining the study diet, nutritional assessment, adherence to the diet, measurements, advice and instruction in case of possible side effects.

Nutritional assessment

Nutritional assessment will take place during the study visits at the outpatient clinic and consists of:

- Resting energy expenditure (Indirect calorimetry)
- Body composition by bioelectrical impedance analysis (BIA)
- 3-day food diary filled in at home and cross checked during the study visits.
- Anthropometric measurements, body weight will be measured during visits to the outpatient clinic.

Nutritional assessment is part of standard dietetic care. For the operational procedures we refer to the NAP website (72). The procedure involves measurement of inspired and expired air. Participants are asked to lay down in a supine position for approximately half an hour and to breath in and out of a ventilated hood. Bio impedance involves the patient to lay down in a supine position or stand on a special scale with special handgrips for 1 minute.

Questionnaires

Questionnaires will focus on adherence and any possible side effects / symptoms subjects might experience during the ketogenic diet. Other questionnaires conducted during study focus on quality of life and physical activity.

Consultation by Clinician / Investigator

This consult will focus on any possible abdominal pain / complaints, any complaints after halting oral contraceptives, advice to currently avoid pregnancy and advice concerning when to contact our outpatient clinic.

Imaging studies

Subjects will receive their follow-up MRI according to normal treatment protocol after 6 months. No additional imaging studies will be performed for this study, extra measurements will be made on already acquired imaging studies to calculate the liver fat content.

Laboratory testing

Blood will be acquired by venous puncture for measuring fasting parameters. Blood sampling will be done thrice, each time 2 tubes of 10ml will be withdrawn.

Urine testing

Ketones / Acetoacetate in urine will be assessed thrice weekly by subjects themselves using a simple urinestrip to determine / confirm ketose state and therefore adherence. Subjects will be carefully instructed during their clinical appointments on how to use these strips.

Followup overview:

Table 2: Study overview, window for appointments: T₁&T₂: +/- 3 days, T₃-T₅: +/- 1 week

Procedure	T ₀ Baseline	T ₁ 2 weeks	T ₂ 6 weeks	T ₃ 3 months	T ₄ 4 months	T ₅ 6 months

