11.2 Recruitment and consent

Participants will be recruited for the trial during their second visit to our outpatient clinic after their referral for additional imaging (on indication) and management of their incidental hepatocellular adenoma. The gastro-enterologist or hepatobiliary surgeon informs the subject about the study procedures and the general outline of the trial. If the subject is interested to be included in the study after the short explanation of their physician, she will be referred to the study investigator or dietician for further information concerning the study design and purpose. Subjects receive written information and are offered a reflection period of one week. It is the responsibility of the investigators to provide the subjects with detailed information, both orally and in writing, about the aims and design of the study, as well as the study procedures involved. The subjects will have the opportunity to ask all possible questions and receive additional information throughout enrolment in this study. Possible participants will be asked to make their decision 1 week after the visit to our outpatient clinic.

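### The baseline MRI has no fixed date and the 6-month MRI has two possible starting points, so tumour regression may be compared over unequal intervals that the primary model does not adjust for

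*Protocol*

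**What the plan says.** Section 8.1.1 defines the primary endpoint through two MRI measurements of the largest adenoma, which "will be measured at T_0 = time of inclusion and at T_5 = 6 months after start of the intervention". The study overview in 8.3 has a single imaging row, for the follow-up MRI, marked at T5 only. The imaging paragraph of 8.3 adds: "No additional imaging studies will be performed for this study".

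The baseline image therefore comes from the clinical work-up. Under 8.3 the centre images the patient "if the necessary imaging study has not been conducted at the peripheral/referring hospital", and the multidisciplinary meeting comes afterwards. Invitation follows that meeting. Section 11.2 states: "Participants will be recruited for the trial during their second visit to our outpatient clinic after their referral for additional imaging". Patients are then "offered a reflection period of one week", and those who consent are given a dietician appointment.

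On the follow-up scan, 8.3 says: "Subjects will receive their follow-up MRI according to normal treatment protocol after 6 months". It does not say from when. Section 4.1 counts the usual surveillance period from diagnosis.

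Scan age is recorded. Section 8.1.3 lists "time since initial diagnosis, time since last imaging study, imaging study provided (MRI/CT/Ultrasound") among the baseline characteristics. For the historical cohort, section 3 names "dates of diagnosis and first follow-up and HCA-subtype" among the inputs of the prediction model. The interval between scans is neither among the matching variables in section 3 nor among the covariates in 10.1.

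**The concern.** The primary analysis compares millimetres of regression between women on the diet and historical controls. That comparison is fair only if both groups are observed over similar intervals, or if the model allows for the difference. The end of the interval is controlled, because T5 has a window of one week either side. The start is open.

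Time matters here because lesions shrink without the diet. The introduction describes regression after contraceptives are stopped, and the historical median fell by 17 mm in 6 months. Extra observation time in one group would look like a treatment effect. Conversely, if the follow-up MRI is timed from diagnosis, some participants would be scanned before completing 6 months of diet. The comparison is not randomised, so nothing in the design balances these differences.

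**Working it through.** **Inputs from the protocol.** Historical medians are 82.0 mm at baseline and 65.0 mm at 6 months, the target is an additional decrease of 13 mm, and 51 subjects are required (section 4.4).

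**The plan's own figures.** The target reproduces: 0.20 × 65 = 13 mm. The protocol states no SD. Taking one from the follow-up interquartile range gives (80 − 56)/1.349 = 17.8 mm. Then n = 2 × (17.8 × (1.960 + 1.645)/13)² ≈ 49 per group by the normal approximation, 50 by t-test, and 51 by t-test with the SD rounded to 18. The stated 51 is thus close to a per-group number, and this point does not change it.

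**Order of events.** Baseline imaging, multidisciplinary meeting, invitation, reflection week, dietician appointment, diet start, T5. The only dated step between scan and diet is the one-week reflection period. Write L for the whole lag in months. L is not given, so a range is assumed.

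**Reading A: the follow-up MRI is 6 months after diet start (8.1.1).** The diet group's scan interval is 6 + L months. Controls are assumed to have exactly 6, and shrinkage before the diet is assumed to run at the historical rate.
- Linear: (82 − 65)/6 = 2.83 mm per month, so the excess is 2.83 × L.
- Proportional: the excess is 65 × (1 − (65/82)^(L/6)).

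**Reading B: the follow-up MRI is 6 months after diagnosis (possible under 4.1 and 8.3).** Taking the baseline scan as close to diagnosis, the scan interval is about 6 months and diet exposure is 6 − L. If a true 13 mm effect built up evenly over 6 months (a further assumption), the part lost is 13 × L/6.

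| Lag L (assumed) | A, linear: spurious gain | A, proportional: spurious gain | B: part of a 13 mm effect lost |
|---|---|---|---|
| 1 week (0.23 months) | 0.65 mm (5% of 13) | 0.58 mm (4%) | 0.5 mm (4%) |
| 1 month | 2.8 mm (22%) | 2.5 mm (19%) | 2.2 mm (17%) |
| 2 months | 5.7 mm (44%) | 4.8 mm (37%) | 4.3 mm (33%) |
| 3 months | 8.5 mm (65%) | 7.1 mm (55%) | 6.5 mm (50%) |

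**Effect on the test under reading A.** With 51 per group, SD 17.8 mm and no diet effect, the standard error is 17.8 × √(2/51) = 3.52 mm. A two-sided 5% z-test then rejects with probability of about 0.05 at 1 week, 0.13 at 1 month, 0.36 at 2 months and 0.68 at 3 months under linear shrinkage (0.05, 0.11, 0.28 and 0.53 under proportional shrinkage). This SD is that of the follow-up diameter. The SD of regression is not in the protocol, so these figures are only indicative.

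**The case against.** A reader might infer that pre-diet shrinkage will be credited to the diet. The documents do not establish that. Section 8.3 keeps follow-up visits as in usual care apart from the added dietician appointments and blood samples, and it times the MRI by the normal protocol. On that reading there is no excess interval, and the error runs against the diet.

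Nor does the protocol show a long lag. Referral, imaging and the multidisciplinary meeting are usual practice, so controls may have had a similar delay. The delay specific to the trial may be little more than the reflection week and an undated appointment, and one week is negligible. The control cohort is retrospective and multicentre, so its intervals may vary around 6 months and the difference could take either sign. The rate of 2.83 mm per month is a difference of medians from a cohort with large lesions, whereas the trial accepts adenomas of any size. When contraceptives were stopped relative to the baseline scan is not stated. All of this stands and limits what can be said about direction and size.

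Two further inferences are tempting and not supported. One is that the baseline scan is the diagnostic scan: section 8.1.3 records time since diagnosis and time since last imaging separately, and imaging may be added after referral. The other is that baseline sizes will come from CT or ultrasound: section 8.1.1 specifies MRI, and the modality item in 8.1.3 may simply record what the referring hospital supplied.

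It can also be said that scan age is collected and that baseline characteristics are compared with controls. This makes an adjustment possible, but the analysis in 10.1 does not include one.

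**Conclusion.** The point holds as an undefined baseline and an unresolved timing conflict in the primary endpoint, with a covariate list that leaves out the scan interval. It does not hold as a demonstrated bias in favour of the diet. The direction depends on which starting point is used for the 6-month MRI, and the size depends on a lag that the protocol does not state. Under reading A the spurious gain is trivial at 1 week. From about 1 month it is material, at roughly a fifth of the 13 mm target. Those figures rest on control intervals of 6 months and on pre-diet shrinkage at the historical rate. Under reading B a real effect would be understated. Because the protocol fixes both the endpoint times and the covariates, the conflict should be settled there before the data are analysed.

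**What to change.** - Reconcile 8.1.1, 8.3 and the study overview on the starting point of the 6-month MRI.
- Define the baseline MRI by one rule, including how old it may be, and apply the same rule to participants and historical controls. A rule for participants alone would create a new mismatch.
- Record the dates of both scans and of diet start.
- Add the baseline-to-follow-up scan interval, in days, as a covariate in the 10.1 model for both groups, or analyse regression per month. Report the distribution of the interval by group: where the groups barely overlap, the adjustment depends on the assumed form of shrinkage.
- Report time on diet at the follow-up MRI. Adjusting for the scan interval does not correct for shortened exposure.
- Do not use the interval as a propensity-score matching variable, since it is known only after baseline.
- If any baseline scan proves not to be an MRI, add a sensitivity analysis limited to MRI-to-MRI pairs.
- Apply the same definitions to the subpopulation, which has the same gap between its surveillance MRI and diet start.

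The cost is some wording, one model term and a small loss of precision. No new scans or visits are needed. Scan age is already recorded for participants, and dates of diagnosis and first follow-up are inputs of the historical model. It should be checked that the control date of diagnosis is also the date of the baseline scan.
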